6.3.2.5. Sacituzumab Govitecan Dose Modification Guidelines

Dose Delays

Sacituzumab govitecan is to be administered in 21-day cycles on Day 1 and Day 8; the next cycle should start a minimum 14 days after the Day 8 dose (ie, the Day 8 infusion will be counted as the first day of that 14-day period). Dosing 1 day prior to and 7 days after the scheduled infusion are permitted. The scheduled Day 1 and Day 8 infusions may be delayed for up to one week for treatment-related toxicities.

Instructions for dose delays and dose reductions for specific toxicities are summarized below. For toxicities not specifically addressed in the toxicity management table ([Table 2](#)), dosing may be delayed for > Grade 2 toxicities for a maximum of one week. If the toxicity has improved to ≤ Grade 2, the dose should be administered at that time. For a toxicity that delays Day 8 dosing, if the toxicity has not resolved to ≤ Grade 2 within one week, dosing should resume with the next scheduled cycle, ie, the next dose will be Day 1 of the following cycle. Regardless of whether the Day 8 dose is delayed for toxicity, there should be a minimum of 14 days between the Day 8 infusion and the Day 1 infusion of the next cycle (day of delay is counted as day 1 of this 14-day period).

Dose Reductions and Discontinuation

The major toxicities of sacituzumab govitecan are expected to be gastrointestinal symptoms and hematologic suppression. All subjects will be closely monitored over the course of their treatment and aggressively medically managed, including dose reduction and interruption, in order to prevent the need for treatment discontinuation and serious complications of these toxicities. All efforts to avoid dose reduction should be taken to address toxicity prior to institution of dose reduction. Sacituzumab govitecan dose reductions and interruptions will be managed based on toxicity severity, as assessed by NCI CTCAE v5.0. Leukopenia or lymphopenia in the absence of neutropenia will not require dose delay or dose modification. The dose of sacituzumab govitecan **must not** be re-escalated following a dose reduction. [Table 2](#) summarizes recommendations for sacituzumab govitecan dose reductions and discontinuations for treatment-related toxicities.

Table 2.

Recommended Dose Modification Schedule for Sacituzumab Govitecan

Adverse Reaction	Occurrence	Dose Modification or Action
Severe neutropenia		
Grade 4 neutropenia \geq 7 days, OR	First	25% dose reduction and administer G-CSF
Grade 3-4 febrile neutropenia, OR	Second	50% dose reduction
At time of scheduled treatment, Grade 3 or 4 neutropenia that delays dosing by 2 or 3 weeks for recovery to \leq Grade 1	Third	Discontinue treatment
At time of scheduled treatment, Grade 3 or 4 neutropenia that delays dosing beyond 3 weeks for recovery to \leq Grade 1	First	Discontinue treatment
Severe nonneutropenic toxicity		
Grade 4 nonhematologic toxicity of any duration, OR	First	25% dose reduction
Any Grade 3 or 4 nausea, vomiting, or diarrhea due to treatment that is not controlled with antiemetics and antidiarrheal agents OR	Second	50% dose reduction
Other Grade 3 or 4 nonhematologic toxicity persisting $>$ 48 hours despite optimal medical management, OR	Third	Discontinue treatment
At time of scheduled treatment, Grade 3 or 4 nonneutropenic hematologic or nonhematologic toxicity that delays dose by 2 or 3 weeks for recovery to \leq Grade 1		
In the event of Grade 3 or 4 nonneutropenic hematologic or nonhematologic toxicity that does not recover to \leq Grade 1 within 3 weeks	First	Discontinue treatment
Infusion-Related Toxicities		
Grade 2 or Grade 3 infusion-related reaction despite optimal management	Recurrent	Discontinue treatment
Grade 4 infusion-related reaction	First	Discontinue treatment

G-CSF = granulocyte colony-stimulating factor; NCI-CTCAE = National Cancer Institute-Common Terminology Criteria for Adverse Events

Refer to Section 10.2.2.6 for the NCI-CTCAE severity grading details.

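### Protocol 6.3.2.5 and Table 2 give toxicity-delay rules that do not fit together, on the length of a Day 1 delay and on the recovery grade for re-dosing

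*Protocol*

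**What the plan says.** The Dose Delays text of Protocol 6.3.2.5 opens with a general sentence: "The scheduled Day 1 and Day 8 infusions may be delayed for up to one week for treatment-related toxicities". It continues: "Instructions for dose delays and dose reductions for specific toxicities are summarized below". It then adds a fallback rule, whose scope is set by this phrase: "For toxicities not specifically addressed in the toxicity management table". The table meant is Table 2. Under the fallback rule, "dosing may be delayed for > Grade 2 toxicities for a maximum of one week", and once the toxicity is at or below "Grade 2, the dose should be administered at that time". If a Day 8 dose is still held after one week, "dosing should resume with the next scheduled cycle, ie, the next dose will be Day 1 of the following cycle". There is no matching sentence for Day 1.

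Table 2 "summarizes recommendations for sacituzumab govitecan dose reductions and discontinuations for treatment-related toxicities". One of its triggers is "Grade 3 or 4 neutropenia that delays dosing by 2 or 3 weeks", with recovery measured to Grade 1 or lower. A parallel row covers Grade 3–4 toxicity that is nonhematologic, or hematologic other than neutropenia. For both, the action is a 25% reduction at the first occurrence, a 50% reduction at the second and discontinuation at the third. Separate rows call for discontinuation at the first occurrence when a neutropenia delay runs past 3 weeks, or when another Grade 3–4 toxicity has not recovered to Grade 1 or lower within 3 weeks.

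Two other sections set holds. Protocol 6.3.2.2 withholds dosing for Grade 3 nausea and Grade 3–4 vomiting or diarrhea until Grade 1 or lower. Protocol 6.3.2.3 sets neutrophil thresholds for dosing. Neither gives a maximum delay.

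**The concern.** Two things do not fit.

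- **Length of a Day 1 delay.** The general sentence gives one week for treatment-related toxicities. Table 2, for the same class, takes for granted that a subject can be delayed 2 or 3 weeks and then continue at a lower dose. The one-week sentence carries no exception for Table 2 or for the holds in 6.3.2.2 and 6.3.2.3.
- **Recovery grade.** The fallback rule uses Grade 2 or lower; Table 2 uses Grade 1 or lower. Which applies turns on whether Table 2's broad rows count as specifically addressing a toxicity they do not name individually. The protocol does not say.

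The possible actions are hard to undo. Section 6.3.2.5 forbids re-escalation after a reduction, and discontinuation ends therapy for subjects enrolled because they are benefiting. The summaries of delays and reductions in SAP 6.1, and of AEs leading to reduction, interruption or discontinuation in SAP 6.2, will reflect whichever reading each site adopts.

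**Working it through.** There is no planned figure to reproduce. The check sets the passages side by side and does calendar arithmetic on the 21-day cycle.

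**1. Day 1 delay.** Inputs: 7 days (6.3.2.5 text); 2 or 3 weeks, that is 14 or 21 days (Table 2).
- 14 − 7 = 7 days past the one-week sentence at the 2-week trigger.
- 21 − 7 = 14 days past it at the 3-week trigger.

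A Day 1 delay long enough to meet Table 2's delay rows is therefore always longer than the general sentence allows.

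**2. Day 8 delay.** With Day 1 as day 1, the next cycle starts on day 22. Counting from the scheduled Day 8:
- Dose moved to the next Day 1: 22 − 8 = 14 days.
- That Day 1 then delayed one week: 29 − 8 = 21 days.

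These intervals fall on Table 2's 2 and 3 weeks, so Day 8 can be read consistently with both texts. The mismatch in length concerns Day 1.

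**3. Which text governs a Day 1 delay?**
- Pointing to Table 2 and the specific holds: the sentence promising instructions for specific toxicities; the one-week maximum being repeated only for toxicities outside Table 2; the open-ended holds in 6.3.2.2 and 6.3.2.3; and Protocol 5.3, which lists no discontinuation for a prolonged Day 1 delay as such.
- Pointing the other way: the general sentence is unqualified, and Table 2 is introduced as covering reductions and discontinuations, not delays.

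The first reading is the likelier one for named toxicities, but it has to be inferred.

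**4. What is left for the fallback rule?** It covers toxicities above Grade 2, which for a subject still on treatment means Grade 3 or 4. Table 2's delay rows cover Grade 3–4 neutropenia, other hematologic toxicity and nonhematologic toxicity.
- If the broad rows count as specifically addressing a toxicity, these three classes leave almost nothing for the fallback.
- If they do not count, a toxicity not named individually, such as anemia, falls under both rules.

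**5. Example under the second reading (hypothetical).** Treatment-related anemia is Grade 3 at a scheduled Day 1, Grade 2 seven days later, and still Grade 2 at day 21.
- Fallback rule: Grade 2 is reached at day 7, so the dose is given then.
- Table 2: no recovery to Grade 1 or lower within 3 weeks, so treatment is discontinued at the first occurrence. This row is not worded as depending on a dosing delay.

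The two actions are 21 − 7 = 14 days apart and opposite in direction. For anemia, Table 2 implies withholding until Grade 1 but does not state it.

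**The case against.** The best case for the plan is that this is a graduated scheme. The one-week sentence is general and permissive, the specific rules follow it, and a universal one-week cap would make both the fallback wording and Table 2's delay rows pointless. Anemia plainly belongs to a class Table 2 names, so only Table 2 applies, and a fallback with little left to cover is redundant, not contradictory. The fallback also lacks the treatment-related qualifier used to introduce Table 2, so it may have been meant for other events. Finally, Table 2 is headed as recommended, and Protocol 6.3 and 6.3.2 defer to standard practice.

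Much of this stands. It makes Table 2, with 6.3.2.2 and 6.3.2.3, the likelier governing text for named toxicities. It does not remove the unqualified one-week sentence, supply the missing Day 1 step, or say whether the broad rows count. The narrower purpose suggested for the fallback is stated nowhere. Calling rules recommendations does not make them agree.

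Two stronger readings are tempting and not supported:
- **That Day 1 delays of 8 to 13 days have no instruction at all.** Table 2 also has rows triggered by duration: Grade 4 neutropenia of at least 7 days, Grade 4 nonhematologic toxicity of any duration, and other Grade 3–4 nonhematologic toxicity beyond 48 hours despite optimal management. The holds in 6.3.2.2 and 6.3.2.3 continue until their criteria are met. Many such delays therefore do have a stated action; what is left is mainly hematologic toxicity other than neutropenia.
- **That the problem must be frequent because neutropenia and diarrhea most often led to treatment modification.** Protocol 1.3.4 says so, but also says both resolved within about 1 week of onset, and subjects entering this study are tolerating therapy. Long Day 1 delays for these events may be uncommon.

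**Conclusion.** The point holds as an inconsistency between stated rules, with moderate confidence. On length, the text allows 7 days where Table 2 provides for 14 or 21 with treatment continuing. The likely precedence of the specific rules is implied but not written, and the step after one week is given for Day 8 only. On recovery grade, the fallback rule is either nearly empty or conflicts with Table 2 for toxicities not named individually; in the example, the readings differ between re-dosing at day 7 and discontinuing at day 21.

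This rests on reading 2 or 3 weeks as 14 or 21 days, and on counting the example's 3 weeks from the scheduled Day 1. The documents give no rate from which to count affected subjects. A reader might infer that the primary endpoints in Protocol 11.3.1 are compromised. They are not directly affected: they are percentages with any AE, any SAE or any laboratory abnormality. The exposure summaries and the summaries of AEs leading to dose changes are the ones that depend on the rule each site applies.

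**What to change.** The sponsor's clinical team should reconcile the Dose Delays text of Protocol 6.3.2.5 with Table 2 and with Sections 6.3.2.2 and 6.3.2.3. The revised wording should:

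- limit the one-week sentence to the toxicities it is meant for, or align it with the other rules;
- state what governs a Day 1 delay beyond one week;
- state whether Table 2's broad rows count as specifically addressing a toxicity they do not name, and therefore when the fallback rule applies.

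No delay limit, grade or dose is proposed here; those are clinical decisions. The cost is a protocol clarification, with no added procedures or data collection.

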6.4. Concomitant Medications

Medications initiated prior to the first dose of study drug will be recorded as prior medications with medications initiated following receipt of the first dose of study drug until 30 days after treatment discontinuation will be captured as concomitant medications. Medication information will be entered in the appropriate eCRF with information regarding dose, indication, route of administration and dates of administration. Medications used for prophylaxis of anticipated study drug adverse events as outlined in the protocol should be documented with rationale for prophylactic intent.

Subjects must avoid the use of osteopathic traditional medicine and any other traditional medicine during the study.

No anti-cancer therapies, aside from the study drug are permitted during this study. However, palliative and/or supportive medications, such as pain medications, bone modifying-medications (bisphosphonates or denosumab), anti-emetics or anti-diarrheal medications, transfusions and growth factor support are allowed at the investigator's discretion. Palliative radiotherapy is permitted.

Treatment may be continued after completion of palliative radiotherapy. In this case, sacituzumab govitecan administration should be interrupted one week before the procedure and reinstated no earlier than two weeks after the procedure. In the event that a subject requires surgery, sacituzumab govitecan should be interrupted one week before the procedure if clinically feasible and dosing should be held for 2 weeks after the procedure. Dosing may resume thereafter if the subject is clinically stable. Extensive surgical procedures such as abdominal, cranial surgeries for example, may require suspension of dosing for 4 weeks before dosing may resume to allow for an adequate period for healing.

The study medical monitor must approve continuation of therapy with sacituzumab govitecan prior to resumption of dosing.

Subjects are allowed to receive the COVID-19 vaccine to reduce the risk and complications of COVID-19 infection. Details on the risk assessment and mitigation plan for concurrent administration of the COVID-19 vaccine are provided in [Appendix 2](#).

6.5. Drug Interactions

No formal drug-drug interaction studies with sacituzumab govitecan have been conducted. SN-38 (the active metabolite of sacituzumab govitecan) is metabolized via human UGT1A1. Concomitant administration of inhibitors or inducers of UGT1A1 with sacituzumab govitecan should be avoided due to the potential to either increase (inhibitors) or decrease (inducers) the exposure to SN-38, unless there are no therapeutic alternatives.

6.5.1. UGT1A1 Inhibitors

Co-administration of sacituzumab govitecan with inhibitors of UGT1A1 (eg, atazanavir, gemfibrozil, indinavir) may increase systemic exposure to the active metabolite, SN-38. Do not administer UGT1A1 inhibitors with sacituzumab govitecan unless there are no therapeutic alternatives. A list of example UGT1A1 inhibitors is provided in [Appendix 5](#).

6.5.2. UGT1A1 Inducers

Exposure to SN-38 may be substantially reduced in subjects concomitantly receiving UGT1A1 enzyme inducers. Do not administer UGT1A1 inducers with sacituzumab govitecan unless there are no therapeutic alternatives. A list of example UGT1A1 inducers is provided in [Appendix 5](#).

6.6. Treatment Compliance

Sacituzumab govitecan will be administered at scheduled study centers under the supervision of the Investigator or sub-Investigator(s). The pharmacist will maintain records of study drug receipt, preparation, and dispensing, including the applicable lot numbers, subject's weight, and total drug administered in milligrams. Any discrepancy between the calculated dose and dose administered and the reason for the discrepancy must be recorded in the source documents.

7. STUDY DRUG MATERIALS AND MANAGEMENT

7.1. Study Drug

The Investigational Medicinal Product (IMP) is supplied as a sterile, off-white to yellowish lyophilized powder in single-dose glass vials. It is formulated in 2-(N-morpholino)ethane sulfonic acid (MES) buffer containing trehalose and polysorbate 80 and contains no preservatives. Following reconstitution, the concentration of the IMP is 10 mg/mL. The pH of the reconstituted solution is approximately 6.5.

7.2. Study Drug Packaging and Labeling

Vials are intended for clinical use only and the label includes the study name or code, name of the IMP, lot number, strength and expiration date, as applicable. Sacituzumab govitecan will be supplied in cartons, each containing 1 vial.

7.3. Study Drug Storage

The IMP is photosensitive and should be protected from light during storage, transport, and administration.

All vials of IMP must be stored under refrigeration (2 °C to 8 °C) and protected from light in a locked location that can be accessed only by the study Pharmacist, the Principal Investigator, or other duly authorized persons until administered to the subject. Additional information regarding study drug storage is presented in the Pharmacy Manual.

7.4. Study Drug Preparation

Dose preparation must be documented according to institutional guidelines and all records must be kept in the study file.

The Pharmacist is required to follow the appropriate steps regarding the reconstitution and dilution of the study drug per the Pharmacy Manual.

7.5. Administration

Sacituzumab govitecan is a cytotoxic drug. Follow applicable special handling and disposal procedures.

- Administer IMP as an IV infusion
- Infusions may be administered over 1 to 2 hours if previous infusions were well tolerated.
- Protect the infusion bag from light.
- An infusion pump may be used.

- Compatibility with polypropylene infusion bags has been confirmed.
- Compatibility with in-line filters and other ancillary infusion equipment has not been studied.
- Do not mix IMP, or administer as an infusion, with other medicinal products.
- Upon completion of the infusion, flush the IV line with 20 mL 0.9% Sodium Chloride Injection, United States Pharmacopeia (USP).

7.6. Study Drug Accountability

The IMP must be stored in a locked location that can be accessed only by the Study Pharmacist, the Principal Investigator, or another duly authorized study/site personnel.

The IMP must not be used outside of the context of this protocol. Under no circumstances should the Investigator or other site personnel supply IMP to other Investigators, subjects, or clinics, or allow supplies to be used other than as directed by this protocol without prior written authorization from the sponsor.

Records documenting receipt, use, return, loss, or other disposition of the IMP must be kept. A complete drug accountability record should be maintained. In all cases, information describing study medication supplies and their disposition, subject-by-subject, must be provided and signed by the Investigator (or the pharmacist or other person who dispensed the drug) and collected by the study sponsor or designee. Requisite data include relevant dates, quantities, batches or code numbers, and subject identification for subjects who received IMP.

7.7. Study Drug Handling and Disposal

7.7.1. Study Drug Shipment

The IMP will be shipped at refrigerated temperature in an insulated shipper, protected from light and with a temperature monitoring device. The shipper must be opened immediately upon receipt.

7.7.2. Receipt of IMP

All IMP should be inspected upon receipt as indicated on the Packing List. Follow instructions on the Packing List to complete any necessary forms and report issues or product complaints as directed in the Pharmacy Manual. Sites must retain all IMP vials affected and may not perform any additional testing on the vials in question.

If use of the interactive web-based response system (IWRS) is required, follow the process found in the study-specific IWRS Manual.

The study Pharmacist, or the Principal Investigator or designee must confirm that appropriate conditions have been maintained during transit and that any discrepancies are reported per guidance found in the Pharmacy Manual.

7.7.3. Study Drug Disposal

At the end of the study, or if instructed to do so during the study, the IMP may be destroyed at the site as dictated by the appropriate standard operating procedures at the participating institutions. IMP may not be destroyed until it has been reconciled and written confirmation has been received from the sponsor Study Contact or designee.

Destruction of IMP must be documented.

If local destruction is not possible, the IMP may be returned as per the agreed upon process. Return of IMP must be documented. The sponsor Study Contact or designee assigned to your site will assist with the return of IMP once it has been deemed appropriate by the sponsor.

8. ASSESSMENT OF EFFICACY

Efficacy will not be assessed in this study.

9. OTHER EVALUATIONS

Pharmacokinetics, immunogenicity, and ‘other’ evaluations will not be assessed for this study.

10. ASSESSMENT OF SAFETY

10.1. Safety Parameters

10.1.1. Weight

Weight will be measured as indicated in [Table 1](#).

10.1.2. Laboratory Assessments

All clinical laboratory samples for safety will be collected and analyzed by the site's local laboratory with appropriate clinical action taken based on the Investigator's clinical judgement. All investigations will be assessed for all subjects as indicated in [Table 1](#). Additional and more frequent tests may be performed at the Investigator's discretion. The specific details of each assessment will be recorded on the appropriate eCRF. Clinically-significant abnormal results should be repeated within 24-48 hours or as per treating physician's discretion to confirm abnormality and followed until resolution. The panels of laboratory tests to be performed are detailed below. For subjects rolling over from IMMU-132-15 or any new parent studies in the future, Gilead's standard reference ranges will be used.

10.1.2.1. Hematology

Hemoglobin, white blood cell (WBC) count and differential (with ANC), and platelet count to be performed as indicated in [Table 1](#). ANC levels must be confirmed prior to each dose as described in Section [6.3.2.3](#).

10.1.2.2. Serum Chemistry

Total protein, albumin, total bilirubin, alkaline phosphatase (ALP), alanine aminotransferase (ALT), aspartate aminotransferase (AST), creatinine (estimated glomerular filtration rate [GFR] using a validated model, refer to [Appendix 3](#)), blood urea nitrogen (BUN) or urea, glucose, sodium, potassium, magnesium, chloride, bicarbonate, calcium, phosphorus will be obtained for all subjects as indicated in [Table 1](#).

10.1.2.3. Pregnancy Test

In female subjects of childbearing potential, pregnancy testing will be performed according to the Schedule of Assessments ([Table 1](#)) and as presented in [Appendix 4](#).

10.1.2.4. Follicle-Stimulating Hormone

Follicle-stimulating hormone (FSH) testing will be conducted as needed per [Appendix 4](#) for determination of childbearing potential.

